2.5 Risk/Benefit Assessment

Overall, the data from non-clinical studies in non-human species have not revealed any potentially serious toxicities that would preclude the use of umbralisib in patients with hematologic malignancies. Further, data from the ongoing studies of umbralisib has not revealed any unexpected safety trends, and umbralisib has been well tolerated up through 1200 mg QD of the micronized formulation, with patients now on umbralisib for durations in excess of four-years; however long term safety data is only available from a limited number of patients, and should therefore be cautiously extrapolated to other target populations. Considering the clinical activity demonstrated by the class of PI3K δ inhibitors to date, along with the preliminary activity demonstrated by umbralisib thus far, in conjunction with manageable safety profile, the potential benefit-risk ratio of umbralisib is anticipated to be positive in patients with hematologic malignancies. Upon the administration of ublituximab to subjects with CD20-positive lymphoproliferative disorders, one should be aware of the AEs reported in the safety data from the completed and ongoing Phase I studies with ublituximab and the known side-effects reported thus far with other anti-CD20 monoclonal antibodies.

Preliminary safety profile of ublituximab has been inferred from two Phase I studies in advanced stage subjects with CLL and lymphoma exposed to 4 to 8 weekly infusions of the product, and from a limited number of B-Cell Lymphoma subjects exposed to ublituximab in combination with other anti-cancer agents for longer durations. It should therefore be cautiously extrapolated to other target populations and other schedules of ublituximab infusions and or combinations. Taking into account the above mentioned risks, special attention has to be focused on management of acute infusion-related reactions and monitoring of complete blood cell count in order to detect and treat if necessary early or late episodes of neutropenia. In conclusion, considering the more active pre-clinical profile of ublituximab compared with rituximab in B-cell lymphoproliferative disorders, the rapid, profound and sustained blood lymphocyte depletion, the interim assessment of response and the manageable toxicity observed in the Phase I and II studies, the potential benefit-risk ratio of ublituximab is anticipated to be positive in subjects with B-cell malignancies.

3. Subject Selection

3.1 Study Population

Subjects with a diagnosis of CLL/SLL and who have had progressive disease on either a BTK inhibitor, BCL-2 inhibitor, or combination regimen containing one or both of those two classes of drugs will be eligible for participation in this study. Subjects who have received each class of drug in any sequence will be eligible to enroll.

3.2 Inclusion Criteria

A subject will be eligible for participation in the study if he/she meets the following criteria:

1. Subject must have confirmed diagnosis of CLL/SLL and a treatment indication based upon 2018 International Workshop on CLL (IWCLL) criteria.
2. Subject must have documented disease progression on a BTK and or BCL-2 containing regimen as the most recent prior line of therapy. Subjects who were treated with a regimen containing both classes of novel agents will be allowed to enroll and will be enrolled into Cohort B.

Subjects who receive a temporizing non-experimental treatment for up to 2 cycles such as monotherapy with an anti-CD20 monoclonal antibody or corticosteroids including high dose methylprednisolone immediately after progression on a BTK or BCL-2 inhibitor will be considered for enrollment after discussion with the study sponsor.

3. Subject must be ≥ 18 years of age.
4. Subject must have an Eastern Cooperative Oncology Group performance status of ≤ 2 .
5. Subject must have adequate bone marrow function and meet the below thresholds.

- a. Absolute neutrophil count of ≥ 750 cell/ μ L in absence of G-CSF for 7 days prior to enrollment.
 - b. Platelet count of $\geq 30,000$ cells/ μ L independent of transfusion for 21 days prior to enrollment
6. Subject must have adequate organ function and meet the thresholds below:
 - a. Total bilirubin ≤ 1.5 times the upper limit of normal (ULN). Subjects with bilirubin exceeding this limit due to Gilbert's disease are eligible.
 - b. Alanine aminotransferase (ALT) and aspartate aminotransferase (AST) $\leq 2.5 \times$ ULN if no liver involvement or $\leq 5 \times$ the ULN if known liver involvement
 - c. Creatinine clearance >30 ml/min/1.73m² as calculated by the MDRD equation.
7. Ability to swallow and retain oral medication.
8. Female subjects who are not of child-bearing potential (see Appendix: CONTRACEPTION GUIDELINES AND PREGNANCY), and female subjects of child-bearing potential who have a negative serum pregnancy test within 3 days prior to initial trial treatment. Male subjects of reproductive potential may not participate unless they agree to use medically acceptable contraception. Female subjects of child-bearing potential and all male partners, and male subjects must consent to use a medically acceptable method of contraception throughout the study period and for 4 months after the last dose of study drug.
9. Willingness and ability to comply with trial and follow-up procedures, and give written informed consent.

3.3 Exclusion Criteria

A subject will be ineligible for the study if he/she meets any of the following criteria:

1. Subject has had prior exposure to a PI3K inhibitor at any point in treatment history.
2. Subject has discontinued the BTK or BCL2 inhibitor due to intolerance. Intolerance will be defined as discontinuing prior BTKi or BCL-2 therapy for any reason without evidence of progression. Subjects who were re-challenged after discontinuation for therapeutic reasons will be allowed if the toxicity did not recur or was managed without indication for discontinuation. Subjects who progress on BTKi or BCL-2 therapy who were on a reduced dose due to an AE/intolerance are eligible as long as progression has been documented on that reduced dose.
3. Subject has clinical or radiographic evidence of, or has biopsy proven Richter's transformation or prolymphocytic leukemia.

4. Subject has undergone an allogeneic stem cell transplant.
5. Subject has received an autologous hematologic stem cell transplant within 6 months of study entry.
6. Malignancy within 3 years of study enrollment except for adequately treated basal, squamous cell carcinoma or non-melanomatous skin cancer, carcinoma in situ of the cervix, superficial bladder cancer not treated with intravesical chemotherapy or BCG within 6 months, localized prostate cancer and PSA <1.0 mg/dL on 2 consecutive measurements at least 3 months apart with the most recent one being within 4 weeks of study entry.
7. Subject is known to be positive for HIV.
8. Subject has history of hepatitis C infection, active infection with hepatitis B or active cytomegalovirus (CMV) as determined by PCR.
9. Previous exposure to a BTK or Bcl-2 inhibitor therapy within 14 days of initiating study treatment on Cycle -1 Day 1, or previous exposure to anti-cancer therapy including chemotherapy, radiotherapy, or investigational therapy, including other investigational targeted small molecule agents within 21 days of initiating study treatment on Cycle 1 Day 1.
10. Evidence of ongoing systemic bacterial, fungal or viral infection, except localized fungal infections of skin or nails.
11. History of anaphylaxis (excluding infusion related reactions) in association with previous anti-CD20 administration.
12. A known history or active autoimmune disease even if not requiring systemic immunosuppression. Subjects with known history of immune thrombocytopenic purpura or autoimmune hemolytic anemia secondary to CLL are allowed to enroll.
13. Malabsorption syndromes.
14. Irritable bowel syndrome with greater than 3 loose stools per day as a baseline.
15. Any severe and/or uncontrolled medical conditions or other conditions that could affect participation in the study such as:
 - a. Symptomatic, or history of documented congestive heart failure (New York Heart Association functional classification III-IV)[see Appendix: NYHA Classifications]
 - b. Significant cardiovascular disease such as uncontrolled or symptomatic arrhythmias, CHF, or myocardial infarction within 6 months of enrollment.
 - c. Concomitant use of medication known to cause QT prolongation or torsades de pointes should be used with caution and at investigator discretion.

- d. Poorly controlled or clinically significant atherosclerotic vascular disease including cerebrovascular accident (CVA), transient ischemic attack (TIA), angioplasty, cardiac or vascular stenting within 6 months of enrollment.
16. Females who are pregnant or lactating.

4. Registration Procedures

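### The PSA limit in the prostate-cancer exception is given in mg/dL; read literally it equals 10,000 ng/mL and does not discriminate at any PSA below that value

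*Combined protocol and SAP*

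**What the plan says.** Section 3.3, exclusion 6, removes subjects with a second cancer in the recent past: "Malignancy within 3 years of study enrollment except for adequately treated basal, squamous cell carcinoma or non-melanomatous skin cancer", followed by further exceptions. The last of these is "localized prostate cancer and PSA <1.0 mg/dL on 2 consecutive measurements at least 3 months apart", completed by a recency condition, "with the most recent one being within 4 weeks of study entry". Exclusion 15 in the Protocol Summary carries the same exception, with the same number and the same unit.

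Neither place gives a conversion or an alternative unit. PSA appears neither in the schedule of trial events (Section 5.1, Table 1) nor in the screening list (Section 5.1.1), so no other part of the document clarifies what was meant. Section 4.1 requires a checklist signed by the investigator and the research nurse, with redacted source documents that verify eligibility, before a subject is registered.

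**The concern.** The exception is built to be strict. It asks for two successive PSA values, a minimum interval between them and a recent last value. That construction makes sense only if the PSA value is meant to tell quiescent disease from active disease. A limit of 1.0 mg/dL does not fit that purpose, because it is a very large concentration for a quantity that laboratories ordinarily report in ng/mL. The reporting unit is general knowledge and is not stated in the documents.

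This is an operative threshold that the site has to document, and it can go wrong in two ways. If staff apply the unit as written, a subject with uncontrolled localized prostate cancer meets the PSA condition. If they silently read the limit in the laboratory's unit, they apply a rule that the protocol does not contain, and a subject refused on that reading may satisfy the written criteria. Either way, the eligibility record and the protocol disagree.

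**Working it through.** **Inputs**

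- PSA limit: below 1.0 mg/dL (Section 3.3, exclusion 6; the same in Protocol Summary, exclusion 15).
- Exclusion that the exception relaxes: malignancy in the 3 years before enrollment (same items).
- Testing conditions: "on 2 consecutive measurements at least 3 months apart" and "with the most recent one being within 4 weeks of study entry".

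The plan gives no derivation of the limit, so there is no figure of its own to reproduce. The check is a unit conversion.

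**Conversion**

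1 mg = 1,000,000 ng and 1 dL = 100 mL, so

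1.0 mg/dL = 1.0 × 1,000,000 / 100 ng/mL = 10,000 ng/mL.

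In the other direction, if the same number had been meant in ng/mL (an assumption),

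1.0 ng/mL = 1.0 × 100 / 1,000,000 mg/dL = 0.0001 mg/dL.

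The two readings differ by 1.0 / 0.0001 = 10,000-fold.

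**Values put through the criterion as written**

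| PSA (ng/mL) | PSA (mg/dL) | Below 1.0 mg/dL? |
|---|---|---|
| 0.1 | 0.00001 | yes |
| 1 | 0.0001 | yes |
| 4 | 0.0004 | yes |
| 10 | 0.001 | yes |
| 20 | 0.002 | yes |
| 100 | 0.01 | yes |
| 1,000 | 0.1 | yes |
| 5,000 | 0.5 | yes |
| 9,999 | 0.9999 | yes |
| 10,000 | 1.0 | no |

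The criterion first fails at 10,000 ng/mL.

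**Which parts of the exception depend on the unit**

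| Condition | Depends on the unit? |
|---|---|
| Disease is localized | no |
| Two consecutive PSA measurements exist | no |
| They are at least 3 months apart | no |
| The latest is within 4 weeks of study entry | no |
| Each value is under the limit | yes |

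Only the last row is affected.

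**The case against.** The best defence is that the slip is harmless in practice. If the laboratory reports ng/mL, staff will most likely compare the reported number with 1.0 and get the intended result. Wrong admission would require someone to convert the result and then pass a very high value. The checklist itself is not in the documents, so its wording is unknown. Other safeguards also remain: exclusion 15 in Section 3.3 covers severe or uncontrolled conditions, exclusion 9 imposes a 21-day washout from other anti-cancer treatment, and registration information is reviewed centrally. The two lists also agree with each other, so this is not an internal contradiction.

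Most of that stands, and it limits the likely consequence. It does not rescue the text. The defence works only if staff substitute a unit that the protocol does not give, and none of the other safeguards supplies a PSA limit.

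A reader might infer more than the documents support, in three ways.

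- *That the malignancy exclusion has no effect for localized prostate cancer, or that the limit can screen out nobody.* A subject without two suitably spaced and recent measurements is still excluded, and so is one whose recent prostate cancer is not localized. Values of 10,000 ng/mL or more would also fail. That localized disease never reaches them is an outside assumption.
- *That response and survival results will be distorted.* The exception covers only localized disease, so nodal spread at entry falls outside it, and confusion with new nodes under Section 9.1.3 is speculative. PFS and OS are exploratory (Section 1.3) and descriptive (Section 11.2.2).
- *That a measurable share of a cohort is at risk.* One subject in 12 is 1/12 = 8.3%, but that is the weight of any single subject. The documents give no basis for estimating how many, if any, would be wrongly admitted.

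**Conclusion.** The point holds for the numeric limit only. As written, the PSA threshold in both eligibility lists equals 10,000 ng/mL and does not discriminate below that value, so it cannot do the work that the two-measurement rule implies. The localized-disease, number-of-tests and timing conditions continue to operate.

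The conversion is exact and rests on no assumption. That the unit is an error, and not a deliberate choice, is an inference from the mismatch between a demanding testing rule and a limit that hardly binds; general knowledge of how PSA is reported supports it. That ng/mL was meant is likely but unconfirmed.

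The effect is confined to eligibility and to the safety of subjects with a second cancer. The 12 subjects per cohort, the Clopper-Pearson intervals in Sections 11.2.1 and 11.2.2 and the planned analyses are untouched. The correction is still worth making, because the threshold has to be verified for registration and the change costs almost nothing.

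**What to change.** The sponsor should confirm both the intended PSA unit and the intended numeric limit. No limit is proposed here. Once they are confirmed, Section 3.3 exclusion 6, Protocol Summary exclusion 15 and the eligibility checklist used under Section 4.1 should be corrected together, so that all three carry the same number and unit.

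The cost is a small text correction in two places and a matching check of the checklist, made through the protocol's usual amendment route. No procedure, visit, sample size or analysis has to change.

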- a. CMP includes a Basic Metabolic panel (Sodium, potassium, chloride, bicarb, blood urea nitrogen, creatinine, calcium, glucose) and a Hepatic function panel (protein total, albumin, globulin, alanine aminotransferase, aspartate aminotransferase, total bilirubin, alkaline phosphatase), Uric acid required only at screening, C-1 D1, C-1 D15, C1 D1, and C1 D2.
- b. Hepatitis antibody screening will consist of Hepatitis A ab, HBsAg, HBcAb, Hepatitis C Ab. If HBcAb is positive, an HBV DNA PCR should be performed.
- c. B-HCG pregnancy testing required only for females of child bearing potential (FCBP). At screening should be tested by serum within 3 days prior to C-1 D1.
- d. Adverse events should be assessed up to 30 days post last dose. For all serious adverse events (SAE), concomitant medications should be assessed and appropriately captured/reported.
- e. CT neck, chest, abdomen, pelvis with contrast. Radiologic evaluation during follow-up should occur every 12 months or as clinically warranted to document disease progression.

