5.2. Treatment Administration

All treatment will be administered on an outpatient basis. See section 5.2.1 and 5.2.2 for special precautions relevant for each specific study agent administration. All therapy will be administered in cycles with each cycle consisting of 28 days.

Enrolled subjects will initiate umbralisib monotherapy for a one cycle lead-in defined by Cycle -1. This cycle is designed to allow for correlative assay sample collection to assess early clonal shifts after umbralisib therapy. Without the lead-in these shifts may otherwise be masked by peripheral elimination of circulating tumor cells by anti-CD20 therapy. Subjects will be monitored closely upon initiation with a C-1D15 visit to assess tolerability of umbralisib monotherapy. Upon completion of Cycle -1 subjects will then continue on daily umbralisib and initiate combination therapy with ublituximab (U2). Ublituximab administration and induction/continuation is defined in Section 5.2.1. Ublituximab will only be administered through Cycle 6 (i.e no maintenance administration). Starting at C7D1 enrolled subjects will continue on umbralisib monotherapy. Umbralisib will be given on a continuous once daily basis starting at Cycle -1 for each 28 cycle until disease progression, discontinuation due to toxicity, subject death, subject withdrawal of consent, or investigator withdrawal. Administration schedule and timing of umbralisib administration in relation to ublituximab are further defined in Section 5.2.3. The overall treatment administration is depicted in the schema below Figure 1.

Subjects will be evaluated for objective response after completion of 6 cycles of combination therapy. Subjects with a response \geq PR will be allowed to continue on study (umbralisib monotherapy maintenance). A subject that does not meet objective response criteria by IwCLL 2018 guidelines outlined in Section 9.1 at C7D1 must be taken off study. See section 5.4.1 for further details in management of these subjects not meeting strict response criteria after completion of combination therapy.

Figure 1. Study Drug Administration Schema

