5.2.3 Umbralisib

Umbralisib will be administered orally as four 200mg capsules taken once daily for a total daily dose of 800mg. Umbralisib should be taken within 30 minutes of starting a meal. All subjects will initiate a one cycle lead in prior to starting combination therapy with ublituximab, subjects will initiate taking umbralisib on Cycle -1 day 1 through Cycle -1 day 28. Starting on Cycle 1 day 1, subjects may take the dose of umbralisib before or after infusion with ublituximab but umbralisib must be taken within 30 minutes of starting a meal. Subjects will continue daily oral dosing of 800mg umbralisib for 28 days which will constitute a cycle. Subjects should try to take the drug at the same time each day throughout the trial. Subjects should be instructed to swallow the tablets whole and should not chew or crush them. If a dose of umbralisib is missed, it should be taken as soon as possible on the same day. If it is missed for a period of greater than 12 hours, it should be skipped for that day. If vomiting occurs, no attempt should be made to replace the vomited dose. Subjects will continue daily dosing of umbralisib until disease progression, toxicities, or study completion whichever comes first.

Subjects will be eligible to start a new cycle of either combination or monotherapy of umbralisib unless they are experiencing toxicity requiring treatment delay as outlined in Section 6.2 Table 4.

Umbralisib will be dispensed at the sites by the research coordinator or designee under the direction of the PI or by a pharmacist at the site. Before dispensing, the site pharmacist or authorized designee must check that the umbralisib is in accordance with the product specifications and the validity is within the re-test date. Immediately inform TG Therapeutics, Inc. at [contact] with any product quality concerns or questions.

Subjects must be provided drug in its original container. Subjects will be dispensed sufficient umbralisib for roughly 1 cycle of treatment. If the interval between visits is greater than 1 cycle, subjects may be given more than 1 cycle of umbralisib so that they do not have to return between scheduled visits. Subjects should be instructed to return all empty and partially filled bottles including any unused tablets when they return to the site. Study drug compliance should be reviewed with the subject at the beginning of each new treatment cycle and as needed.

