11.4 Reporting and Exclusions

11.4.1 Evaluation of Toxicity

All patients will be evaluable for toxicity from the time of their first treatment with ublituximab or umbralisib. If a subject comes off study due to an adverse event, the subject will be followed for 30 days or until resolution of the toxicity to baseline grade, whichever is longer.

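### The 21-day washout for other anti-cancer therapy is tied to Cycle 1 Day 1, although study treatment starts 28 days earlier, on Cycle -1 Day 1

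*Combined protocol and SAP*

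**What the plan says.** Exclusion 9 (section 3.3) puts two washouts in one sentence. The first is for the targeted agents: "Previous exposure to a BTK or Bcl-2 inhibitor therapy within 14 days of initiating study treatment on Cycle -1 Day 1". The second covers chemotherapy, radiotherapy, investigational drugs and other anti-cancer treatment, and excludes exposure "within 21 days of initiating study treatment on Cycle 1 Day 1". Item 18 of the Protocol Summary has the same two limbs and the same two anchors.

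The treatment sections leave no doubt about the first dosing day. Section 5.2: "Enrolled subjects will initiate umbralisib monotherapy for a one cycle lead-in defined by Cycle -1". Section 5.2.3: "subjects will initiate taking umbralisib on Cycle -1 day 1 through Cycle -1 day 28". The Protocol Summary gives the lead-in as 28 days, and section 5.2 has the combination follow directly, with no Cycle 0.

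Elsewhere the protocol also treats Cycle -1 Day 1 as the start. Inclusion 8 (section 3.2) asks for "a negative serum pregnancy test within 3 days prior to initial trial treatment", and footnote c to Table 1 (section 5.1) places the same test on the calendar: "At screening should be tested by serum within 3 days prior to C-1 D1".

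No other numerical washout for chemotherapy, radiotherapy or investigational agents appears in the documents.

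**The concern.** Both limbs speak of initiating study treatment, yet they give different days for it. Only one can be right, and sections 5.2 and 5.2.3 show that it is Cycle -1 Day 1. A screener who goes by the cycle label, the most specific term in the clause, applies a window that opens a week after the first umbralisib dose. It then restricts nothing before treatment, and it falls in a period when section 5.3 already prohibits other anti-cancer therapy.

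At stake is how clean the lead-in is. Section 11.4.1 states: "All patients will be evaluable for toxicity from the time of their first treatment with ublituximab or umbralisib". Toxicity is therefore counted from Cycle -1 Day 1. Section 5.2 explains the mid-lead-in visit: "Subjects will be monitored closely upon initiation with a C-1D15 visit to assess tolerability of umbralisib monotherapy". Late effects of treatment given shortly before could be taken for umbralisib toxicity at that visit. Attribution has consequences for dosing: after Table 4, the protocol does not allow umbralisib to be re-escalated after a reduction for drug-related toxicity, unless the event is later judged unrelated.

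**Working it through.** The check is a day count. No sample-size, power or interval formula is involved.

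**Inputs**
- First umbralisib dose: Cycle -1 Day 1 (sections 5.2, 5.2.3). Call this day 0.
- Lead-in: 28 days (Protocol Summary), followed directly by Cycle 1 (section 5.2).
- Washout for other anti-cancer therapy: 21 days (exclusion 9; Protocol Summary item 18).
- Convention: a dose exactly 21 days before the anchor counts as inside the window. This is an assumption, used for both readings.

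**Anchor days**
- Cycle -1 Day 15 = day 14.
- Cycle 1 Day 1 = 0 + 28 = day 28.

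**Reading 1: follow the cycle label**
- Window = (28 - 21) to (28 - 1) = day 7 to day 27, which is Cycle -1 Day 8 to Cycle -1 Day 28.
- Overlap with days before day 0: 0 days.
- The last pre-treatment day is day -1. It lies 28 + 1 = 29 days before Cycle 1 Day 1, so it is 29 - 21 = 8 days clear of the limit, and therapy on that day passes.

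**Reading 2: follow the words about initiating treatment**
- Window = (0 - 21) to (0 - 1) = day -21 to day -1.
- Pre-treatment days covered: 21. The latest permitted exposure is day -22.

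**Shortest gaps that the washout clause alone allows**

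| From last other therapy to | Cycle label (last exposure day -1) | Cycle -1 Day 1 anchor (last exposure day -22) |
|---|---|---|
| First umbralisib dose (day 0) | 0 + 1 = 1 day | 0 + 22 = 22 days |
| Cycle -1 Day 15 visit (day 14) | 14 + 1 = 15 days | 14 + 22 = 36 days |

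If day 21 itself is taken as outside the window, each figure in the right-hand column is one day shorter (21 and 35).

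**Sensitivity to a changed lead-in.** If Cycle 1 Day 1 slips by a week (35-day lead-in), the label window becomes day 14 to day 34 and still covers 0 pre-treatment days. It reaches a pre-treatment day only if 21 exceeds the lead-in length, that is, if the lead-in is 20 days or shorter.

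**The case against.** The strongest reply is that the rule is not empty. Its text speaks of initiating study treatment, which can only mean Cycle -1 Day 1, and on those words it works. The label reading is also hard to operate. Section 4.1 requires a signed eligibility checklist with source documents and forbids study drug before registration is confirmed, so nobody can screen a candidate against a window that opens after the first dose. This stands as evidence of intent, and the cause is probably a dropped minus sign. It does not remove the contradiction. Loss of the sign in PDF conversion cannot be excluded, but it is unlikely: the sign survives in the first limb and is missing from the second in both places.

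The second reply is that little exposure is left open, and this largely stands:
- The BTK/Bcl-2 limb is correctly anchored.
- Inclusion 2 requires the BTK or BCL-2 regimen to be the last line before entry, so a separate later line of chemotherapy or investigational treatment is already out.
- Temporizing therapy is limited to 2 cycles and goes through discussion with the sponsor.
- If being on protocol in section 5.3 begins at registration, which the text does not define, therapy between registration and first dose is already barred. The 1-day gap is then an extreme that needs registration and dosing on the same day.

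The third reply is that attribution is protected. Entry requires minimum neutrophil and platelet counts. Blood counts, chemistry and medical history are repeated on Cycle -1 Days 1 and 15, and section 12.2 grades causality on five levels that include unlikely and unrelated. Section 11.4.1 says who is evaluable, not what is attributed to the drug. These safeguards reduce the risk. Laboratory thresholds do not, however, screen for late non-laboratory effects of earlier treatment.

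**Conclusion.** The contradiction is real and appears in both statements of the rule. By the cycle label, the 21-day limb covers 0 pre-treatment days; anchored to Cycle -1 Day 1, it covers 21. The day count rests on a 28-day lead-in and holds for any lead-in of 21 days or more.

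The point is minor. It concerns an operative eligibility rule, but the intended meaning is recoverable from the sentence, and the exposure left open is mainly radiotherapy, partner drugs of the last regimen and temporizing therapy. The consequence is for safety and for attribution of toxicity during the lead-in.

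A reader might infer that the trial has no washout, or that recently treated subjects were enrolled and the response rate in cohorts of 12 is distorted. The documents support neither. The 14-day limb works, nothing shows the label reading being applied, the number of subjects affected cannot be derived, and no shift in response rate can be calculated. No endpoint, sample size or confidence interval depends on this clause.

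**What to change.** In the 21-day limb of exclusion 9 (section 3.3) and of item 18 in the Protocol Summary, replace Cycle 1 Day 1 with Cycle -1 Day 1. The rule then covers days -21 to -1 before the first umbralisib dose and matches the BTK/Bcl-2 limb. The eligibility checklist should carry the same anchor. The 21-day length need not change.

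The cost is one label in two places at the next amendment. The downside is a possible delay of up to about 21 days for a few subjects who need treatment: someone treated the day before a planned first dose would move from a 1-day to a 22-day gap. The existing 21-day rule was evidently meant to impose that delay.
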